We propose a proof-of-concept (phase 2) double-blind randomized placebo-controlled trial to evaluate the efficacy and short-term safety of ramelteon for the prevention of postoperative delirium in a high-risk group of patients, 65 years and older, with MMSE²⁵ scores ≥ 15 , planned orthopedic surgery. Our prior work demonstrates the feasibility of conducting a prevention trial in this population, using state-of-the-art delirium detection and diagnosis methodology.^{5,25} Should this preliminary trial, show evidence of efficacy and adequate safety, then a phase 3 trial will be proposed.

Our group has demonstrated that an early predictor of subsequent delirium is the presence of delirium immediately upon recovery from general anesthesia in the post anesthesia care unit (PACU).^{5,26,27} The proposed trial will incorporate assessment of PACU delirium as a means of early delirium detection in helping to determine the efficacy of the ramelteon intervention.

2. **Objectives (include all primary and secondary objectives)** The proposed trial will involve administering 8 mg ramelteon orally (1 dose preoperatively and 2 doses postoperatively) or placebo in 80 older-aged patients to test the following:

Specific Aim 1 (primary outcome): To compare delirium incidence and severity between ramelteon and placebo using the DSM 5 criteria by expert panel consensus.

Hypothesis 1: Compared to placebo, ramelteon will be associated with a) a lower incidence and severity of postoperative delirium immediately upon recovery from anesthesia in the PACU, and b) with a lower incidence and severity of delirium on postoperative day (POD) 1 and POD 2.

Specific Aim 2 (safety outcome): To compare adverse events (AEs) and serious adverse events (SAEs) between ramelteon and placebo.

Hypothesis 2: Ramelteon will have an adequate safety profile in this postoperative cohort, sufficient to support conducting a larger prevention trial. Specifically, compared to placebo, ramelteon will not be associated with increased incidence of postoperative delirium or with increased adverse side effects including fatigue, headache and next day somnolence during the treatment episode.

3. Background (briefly describe pre-clinical and clinical data, current experience with procedures, drug or device, and any other relevant information to justify the research)

a. Significance:

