The inclusion of a placebo treatment is critical in helping advance our understanding of the effects (both positive and negative) of ramelteon exposure. Placebo comparison is the only way that we can understand what is likely due to ramelteon and what is not.

f. Definition of treatment failure or participant removal criteria.

All consented participants will be retained in the study. Participants with no evidence of riboflavin in the urine sample as tested by fluorescence prior to surgery (i.e. evidence of non-adherence to the first dose of study agent) will continue in the study, receiving second and third doses of study agent, and undergoing delirium outcome measures at all time points; however recruitment will continue until 80 participants with documented adherence to the first doses of study agent is attained. Primary analysis will be intent to treat with all randomized subjects included in the analysis; secondary analysis will include only patients with documented adherence all 3 doses of study medication (a per protocol analysis).

Participants who have their surgery canceled after they have been randomized and who are likely to have surgery in the future will be considered "suspended" from the study. These participants will continue in their assigned condition. A new baseline will be completed prior to their new surgery date to establish that they continue to meet inclusion criteria. The team will proceed with the protocol pre- and postoperatively as assigned during the original randomization. If the participant takes any of the study medication prior to the original surgery, a minimum of 7 days between initial study dosing and the re-initiation of the protocol is required to ensure sufficient time to wash out. If the rescheduled surgery occurs less than 7 days after original dosing, the participant will be excluded from the study.

g. Description of what happens to participants receiving therapy when study ends or if a participant's participation in the study ends prematurely.

Patients will be thanked for their help with the study and will be advised to call the PI with any questions.

5. Inclusion/Exclusion Criteria

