Analysis 2: The continuous DRS-98R severity measure of delirium will be modeled via longitudinal linear regression with correlated observations within participants addressed via the method of GEE with treatment assignment as the covariate of interest and controlling for baseline DRS-98R score, MMSE, surgical duration and sleep disorders.

Data Analysis-Specific Aim 2: Risk of a severe adverse event will be modeled as a function of treatment assignment using logistic regression, as will counts of total adverse events using ordinal logistic regression or Poisson regression as appropriate. Counts of each specific type of AE, as a function of treatment assignment will be scrutinized to determine the power needed to study them in future larger-scale trials.

- d. Early stopping rules. This is a pilot study and will continue until 80 adherent participants are recruited. A Data Safety Monitoring Board will review the data at the end of year one or at recruitment of 40 adherent participants (whichever comes first) to review the unblinded (labelled "A" and "B") data for safety of the intervention. Specifically, for the analyses of rates of delirium in the two groups, we will use a Haybittle-Peto boundary such that the alpha for the interim analysis will be 0.001, and the alpha for the final efficacy analysis will be 0.05.

8. Risks

- a. Medical risks, listing all procedures, their major and minor risks and expected frequency.

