The clinical team (Attending Surgeon - eg., Co-Investigators: [name], [name], [name] and the Chief of Anesthesiology - eg., Co-Investigator [name]) will be notified by the study team should any patient be found to be delirious (thereby ineligible) during the screening process for the study. The Attending Surgeon (or his designee) will be responsible for contacting the patient's family and arranging subsequent follow-up of the patient - either in an emergency setting, in the clinic, or through early admission to hospital. The precise recommendation will be informed by the clinical status of the patient.

- c. Plan for reporting unanticipated problems or study deviations.

All AE's and SAE's will be reported to the IRB and the DSMB in keeping with rules of the Johns Hopkins Institutional Review Board. As noted above – data on adverse effects will be collected each day of the study.

- d. Legal risks such as the risks that would be associated with breach of confidentiality.

As with any study incorporating research as a part of clinical care, there is a small but real risk of unintentional release of HPI. We will make every effort to secure data and study records under lock and key and encryption in keeping with institutional standards to prevent this from occurring.

- e. Financial risks to the participants.

The financial risks to the participants related specifically to this protocol are minimal.

9. Benefits

- a. Description of the probable benefits for the participant and for society.

While there may be no clear benefit for those participants who take part, this study is an important next step in the discovery of pharmaceutical agents in postoperative delirium prevention. **A positive outcome may help relieve suffering of many patients in our healthcare system in the future and stimulate further inquiry delineating the role of melatonin in the genesis of delirium, potentially benefiting society.**

10. Payment and Remuneration

- a. Detail compensation for participants including possible total compensation, proposed bonus, and any proposed reductions or penalties for not completing the protocol.

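### The Aim 2 logistic model for serious adverse events names no sparse-data method, so an arm with no events leaves no finite odds ratio; one sentence would fix it

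*Combined protocol and SAP*

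**What the plan says.** Section 2 sets the safety objective: "To compare adverse events (AEs) and serious adverse events (SAEs) between ramelteon and placebo". Section 7.c, Data Analysis-Specific Aim 2, gives the analysis: "Risk of a severe adverse event will be modeled as a function of treatment assignment using logistic regression". No covariates are named for this model, and nothing says whether inference is by Wald, likelihood-ratio or score test.

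The flexibility in the same sentence concerns a different outcome, the total count of events: "as will counts of total adverse events using ordinal logistic regression or Poisson regression as appropriate". Individual event types are to be inspected rather than tested: "Counts of each specific type of AE, as a function of treatment assignment will be scrutinized to determine the power needed".

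The power paragraph of section 7.c assumes 40 participants per arm. The randomized total can be larger, because section 4.f keeps participants who missed the first dose and says that "recruitment will continue until 80 participants with documented adherence to the first doses of study agent is attained". Adverse events are collected in the PACU and on POD 1 and 2 (assessment table, section 7.a). The documents state no expected rate of serious events.

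**The concern.** The arms are small, the observation window is a few days, and the event may be uncommon, so an arm with no event is a realistic outcome. The maximum-likelihood odds ratio is then infinite or zero. Standard software prints a huge standard error and a Wald p-value close to 1, whatever the other arm shows. The analyst would then have to decide, with the empty arm in view, which p-value to report and what to give in place of an odds ratio. At stake is the readability of the main Aim 2 comparison, and a choice of method that could have been made in advance.

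**Working it through.** **Inputs.** 40 per arm (section 7.c). Two-sided 0.05 is assumed, since no alpha is stated for these events. Event risks of 2%, 5% and 10% are assumed. *Severe* is read as *serious*, to match the objective in section 2.

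**The plan's own figure.** The plan has none for these events. Its delirium power of 0.84 for 30% vs 6% confirms the sample size and alpha. The unpooled standard error is √(0.3×0.7/40 + 0.06×0.94/40) = 0.0816, then 0.24/0.0816 − 1.96 = 0.98, and Φ(0.98) = 0.84.

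**Step 1: how often exactly one arm is empty.** With q = (1 − p)^40, the probability is 2q(1 − q).

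- p = 2%: q = 0.446, giving 49%
- p = 5%: q = 0.1285, giving 22%
- p = 10%: q = 0.0148, giving 3%

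At 50 per arm the figures are 46%, 14% and 1%. Both arms are empty (q²) in a further 20% of trials at 2% risk and 1.7% at 5%. No method can then inform the relative risk.

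**Step 2: p-values for k events against 0, 40 per arm.**

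| Events | Wald | Fisher | Firth | Score | Likelihood ratio |
|---|---|---|---|---|---|
| 3 vs 0 | ≈1 | 0.24 | 0.10 | 0.077 | 0.039 |
| 4 vs 0 | ≈1 | 0.116 | 0.049 | 0.040 | 0.016 |
| 5 vs 0 | ≈1 | 0.055 | 0.023 | 0.021 | 0.007 |
| 6 vs 0 | ≈1 | 0.026 | 0.010 | 0.011 | 0.003 |

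For 4 vs 0, Fisher is 2 × C(40,4)/C(80,4) = 2 × 91,390/1,581,580 = 0.116. The likelihood-ratio statistic is 2[4 ln(4/40) + 36 ln(36/40) − 4 ln(4/80) − 76 ln(76/80)] = 5.76, so p = 0.016. For Wald at 6 vs 0, software returns a standard error of about 12,564 and p = 0.999.

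**Step 3: true type I error at nominal 0.05.** All 41 × 41 tables were enumerated with equal binomial risk in the two arms. Rejections in either direction were counted, and an empty-arm Wald result was counted as not significant.

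| Risk | Likelihood ratio | Firth | Fisher | Wald |
|---|---|---|---|---|
| 2% | 4.1% | 0.7% | 0.01% | <0.01% |
| 5% | 9.1% | 3.8% | 0.4% | 0.05% |
| 10% | 6.5% | 4.5% | 1.7% | 1.2% |

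Over risks from 1% to 30%, the maximum is 9.1% for likelihood ratio and 5.1% for Firth. At 1% risk the likelihood-ratio test rejects in only 1.0% of trials. Its inflation is therefore a mid-range effect, absent at the lowest risks.

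**Step 4: how often the choice of test matters.** With equal risks of 2%, 5% and 10%, an empty-arm table on which two tests disagree about 0.05 occurs in:

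- likelihood ratio against Fisher: 4.1%, 8.0% and 1.7% of trials
- Firth against Fisher: 0.7%, 3.2% and 1.1% of trials

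Under assumed harm (ramelteon vs placebo), the placebo arm is empty and Fisher p is below 0.05 in 9.2% of trials at 10% vs 2%, 7.3% at 15% vs 5% and 1.2% at 20% vs 10%.

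**Step 5: what Firth gives.** With treatment as the only term, the Firth estimate equals the odds ratio after adding 0.5 to each cell. For 6 vs 0 it is (6.5 × 40.5)/(34.5 × 0.5) = 15.3. The 95% profile interval is 1.7 to 2017, and the risk difference is 15.0 points (5.5 to 29.2). For 2 vs 0 it is (2.5 × 40.5)/(38.5 × 0.5) = 5.3 (0.4 to 735), p = 0.22, with a risk difference of 5.0 points (−4.1 to 16.6).

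**The case against.** The plan says logistic regression without qualification, and exact and Firth versions belong to that family. A reader might infer that the plan commits to ordinary maximum likelihood and rules out anything else; it does not. A reader might also infer that an empty arm leaves no usable test. That is not so either, because likelihood-ratio and score p-values can still be computed from the same model. Failure to name the test is also not peculiar to empty arms. At 10% risk, likelihood ratio and Fisher disagree about 0.05 more often in tables without exactly one empty arm (3.1% of trials) than in tables with one (1.7%).

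The step 1 percentages overstate the consequence, because many empty-arm tables are 1 or 2 events against none, which no candidate test calls significant. Under equal risks of 2% and 5%, an empty arm with Firth p below 0.05 occurs in only 0.7% and 3.6% of all trials. At 10% such tables make up a larger share of the empty-arm tables (1.7% of trials out of 3%), but empty arms are then rare.

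The strongest inference to resist is that harm could go unseen, or that stopping or going on to a larger trial depends on this p-value. Counts of event types by arm are planned, and the DSMB sees data split by group (section 7.d). Section 8.c says that adverse and serious adverse events "will be reported to the IRB and the DSMB". Section 8.b does provide for halting on significant harm, but places this under DSMB review. The only numerical boundary, in section 7.d, concerns delirium rates.

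These points stand and limit the concern. What remains is that the planned odds ratio can be infinite, and that no test or substitute estimate has been fixed in advance.

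**Conclusion.** The point holds as a cheap improvement. If exactly one arm has no serious event, the usual fit of the planned model gives no finite odds ratio and a Wald p-value near 1. Among the tests that remain, the likelihood-ratio test is anti-conservative at mid-range risks, and the candidates disagree at 3 to 5 events against none. How likely this is depends on an event rate that the documents do not give: it is a realistic prospect up to about 5% per arm and largely disappears at 10% or more. The conclusion also rests on about 40 per arm and on reading *severe* as *serious*. The effect is on the clarity and pre-specification of one safety comparison in a pilot study, not on whether harm would be detected.

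**What to change.** In Data Analysis-Specific Aim 2, specify Firth-penalised logistic regression for the risk of a serious adverse event, with a penalised-likelihood p-value and 95% interval. Report it with event counts by arm and the risk difference with a 95% Miettinen-Nurminen score interval, and make the risk difference the main readable figure. The same sentence should say *serious* if that is what is meant.

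The cost is one sentence and standard software, with no extra data, visits or participants. There are three downsides:

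- Firth shrinks the odds ratio. For 8 vs 1 it gives (8.5 × 39.5)/(32.5 × 1.5) = 6.9, where maximum likelihood gives (8 × 39)/(32 × 1) = 9.75.
- Its upper limit is very wide when an arm is empty.
- It is less conservative than Fisher in some tables (4 vs 0: 0.049 against 0.116).

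Fisher's exact test with an exact interval, named in advance, would also settle the choice of test. Its true type I error here is at most 1.7% at the three risks examined.

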Outcome Measure Specific Aim I – State-of-the-Art Delirium Assessment and Diagnosis: Well-trained research staff will conduct delirium assessments at baseline, to exclude cases of prevalent delirium, and at three later time points (see Figure and Table). This assessment includes: (1) face to face standardized interview of the patient regarding experiences, (2) standardized cognitive testing including the MMSE⁷⁵ and the abbreviated Digit Span,⁸⁰ (3) history from family/friends familiar with the patient’s cognitive baseline, (4) interview of nursing and other medical staff caring for the patient, and (5) review of medical records for evidence of behavioral disturbances and symptoms in previous 24 hours. Information on sleep disturbance is sought from all sources and is a symptom of delirium. Assessors will rate the CAM⁸¹ and the Delirium Rating Scale-Revised ’98 (DRS-R98)⁶² for the prior 24 hours and describe the patient’s behavior and mental state in a written narrative. If a patient is intubated the CAM-ICU⁸² will be administered to determine delirium status. Patients who are comatose will be documented as such. (Preliminary data suggests that this is a rare occurrence <1%) Final adjudication of delirium diagnosis is derived after all data is presented to a panel of expert delirium diagnosticians ([name]).

The primary diagnosis of delirium is based upon meeting all DSM-5 criteria (see appendix), and is determined by consensus of the expert panel - a method currently employed by this group of co-investigators in the STRIDE study.

A second outcome measure will be analyzed using the continuous variable of delirium severity derived from the DRS-98R severity measure.

Outcome Measure Specific Aim II- Adverse Events: All adverse events (AE and SAE) will be collected from the medical record and daily patient assessment using a customized instrument (“Health Questionnaire”) which will systematically probe for known side effects (fatigue, headache and next day somnolence) (see Protection of Human Subjects). Assessment of Outcome and Covariates:

Table: Timing and Content of Patient Assessments

Assessments	Administration	Collection Instrument and Source
Cognition	Preoperative, PACU POD 1 and 2	Mini Mental State Exam Abbreviated Digit Span: Forwards and Backwards
Delirium	Preoperative, PACU, POD 1 and 2	CAM (full) ⁸³ after patient exam + proxy/medical record review or CAM-ICU if intubated; DRS-98R (severity measure)

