6.1 Clinical Trials Experience

Adverse Reactions Resulting in Discontinuation of Treatment

The data described in this section reflect exposure to ROZEREM in 5373 subjects, including 722 exposed for 6 months or longer, and 448 subjects for one year.

Six percent of the 5373 individual subjects exposed to ROZEREM in clinical studies discontinued treatment owing to an adverse event, compared with 2% of the 2279 subjects receiving placebo. The most frequent adverse events leading to discontinuation in subjects receiving ROZEREM were somnolence, dizziness, nausea, fatigue, headache, and insomnia; all of which occurred in 1% of the patients or less.

ROZEREM Most Commonly Observed Adverse Events

Table 1 displays the incidence of adverse events reported by the 2861 patients with chronic insomnia who participated in placebo-controlled trials of ROZEREM.

Because clinical trials are conducted under widely varying conditions, adverse reaction rates observed in the clinical trials of a drug cannot be directly compared to rates in clinical trials of other drugs, and may not reflect the rates observed in practice. The adverse reaction information from clinical trials does, however, provide a basis for identifying the adverse events that appear to be related to drug use and for approximating rates.

Table 1. Incidence (% of subjects) of Treatment-Emergent Adverse Events

Term	Placebo (n= 1456)	Ramelteon 8 mg (n=1405)
Somnolence	2 %	3%
Fatigue	2%	3%
Dizziness	3%	4%
Nausea	2%	3%
Insomnia exacerbated	2%	3%

b. Steps taken to minimize the risks.

We will adhere to the exclusion criteria listed above which will help avoid the recruitment of patients most at risk of side effects and adverse consequences. Patients will be interviewed each day for any side effects and the medical records will be reviewed and the data collected for Aim 2 of the study. A DSMB will review the data as described above and the study will be halted if there is evidence of harm significantly associated with the intervention. We will also inform participants of the risks – particularly when taking the first dose at home. Specifically we will advise them to call 911 or come to an emergency room if, after taking the study drug, they develop any swelling, rash, difficulty or noisy breathing.

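### Fatigue, headache and next-day somnolence are named in Hypothesis 2 but get counts by arm only, without an effect estimate or interval, and those counts are then meant to inform the power of later trials

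*Combined protocol and SAP*

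**What the plan says.** All references are to the combined protocol and SAP.

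- **Section 2, Hypothesis 2.** The general claim is a safety profile good enough to justify a larger trial. It is then made specific, as a comparison with the control arm: "ramelteon will not be associated with increased incidence of postoperative delirium or with increased adverse side effects including fatigue, headache and next day somnolence".
- **Section 7.a, outcome measure for Specific Aim II.** These three effects are asked about systematically with a purpose-made health questionnaire, so the data will exist.
- **Section 7.c, Data Analysis-Specific Aim 2.** Two quantities are modelled on treatment. The first: "Risk of a severe adverse event will be modeled as a function of treatment assignment using logistic regression". The second: "as will counts of total adverse events using ordinal logistic regression or Poisson regression as appropriate". Counts of each specific event type, by treatment assignment, "will be scrutinized to determine the power needed to study them in future larger-scale trials".

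For the individual event types the section gives no effect measure, confidence interval, margin or description of an acceptable result. Section 7.c states power for delirium incidence and delirium severity, but no power or precision for any adverse event.

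**The concern.** There are two linked gaps.

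First, the hypothesis makes a comparative statement about three named effects, and the analysis stops at a table of counts for them. The modelled total is a weak substitute. In a surgical cohort it pools many unrelated events, and an excess of somnolence could be lost in it. A bare table with similar counts could also be read as reassurance, although 40 per arm cannot exclude a sizeable increase. This matters because Section 1 makes adequate safety a condition for proposing phase 3.

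Second, the stated purpose of the counts is to settle the power of later trials. Counts by arm can serve this in two ways. They can supply a background rate, which is reasonable if its uncertainty is carried along. Or they can supply the effect size, which is not reasonable at this sample size. The text does not say which is meant.

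**Working it through.** **Inputs.** 40 per arm and alpha 0.05 (Section 7.c; sidedness is not stated, so two-sided is assumed). Somnolence and fatigue each 3% on ramelteon 8 mg and 2% on placebo (Section 8.a, package insert, Table 1). Headache is not in that table, and the documents give no postoperative adverse event rates, so higher rates from 10% to 30% are assumptions.

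**The plan's own figure.** Delirium at 30% versus 6%, stated power 0.84:

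- SE = √(0.30×0.70/40 + 0.06×0.94/40) = 0.0816
- 0.24/0.0816 − 1.96 = 0.98, so power = 0.837

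The stated power is reproduced. There is no corresponding figure for adverse events to reproduce.

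**Precision at the package-insert rates.**

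- Expected events: 40×0.03 = 1.2 versus 40×0.02 = 0.8
- SE = √(0.03×0.97/40 + 0.02×0.98/40) = 0.035, or 3.5 points, against a true difference of 1 point
- 95% half-width = 1.96×3.49 = 6.8 points

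**Direction of the observed difference.** Exact binomial enumeration, 40 per arm:

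| True rates, ramelteon vs placebo | More on ramelteon | Tie | Fewer on ramelteon | Tie or wrong direction |
|---|---|---|---|---|
| 3% vs 2% (package insert) | 45.5% | 30.0% | 24.4% | 54.5% |
| 15% vs 10% (assumed) | 69.5% | 10.8% | 19.7% | 30.5% |
| 20% vs 10% (assumed) | 86.7% | 5.7% | 7.5% | 13.3% |
| 30% vs 20% (assumed) | 81.9% | 6.0% | 12.1% | 18.1% |

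At 3% versus 2%, neither arm has any event in 13% of trials.

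**Trial size implied by the observed counts.** For 80% power, n per arm = (1.96 + 0.84)² × (p₁q₁ + p₂q₂)/(p₁ − p₂)², with the squared term equal to 7.849 before rounding.

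- 2/40 versus 0/40: 7.849×0.0475/0.05² = about 149
- 2/40 versus 1/40: 7.849×(0.0475 + 0.0244)/0.025² = about 903
- True 3% versus 2%: 7.849×(0.0291 + 0.0196)/0.01² = about 3,820

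One placebo event more or fewer therefore changes the planned size about sixfold, and both results fall far short of the true requirement.

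At an assumed 20% versus 10%, the true requirement is 7.849×(0.16 + 0.09)/0.10² = about 196. Among trials where the excess is on ramelteon, the implied n has a 10th to 90th percentile range of about 46 to 1,000. A pooled-variance formula gives 49 to 1,004 against 199, which is the same picture.

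**What an interval would show.** Wald half-widths with equal rates in both arms are 13.1 points at 10%, 17.5 at 20% and 20.1 at 30%. Newcombe examples:

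- 2/40 versus 1/40: +2.5 points (−8.5 to +14.2)
- 8/40 versus 4/40: +10 points (−6.1 to +25.9)

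A single-arm rate is also loose: 4/40 has an exact 95% CI of 2.8% to 23.7%.

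**The case against.** The case for leaving the text alone has several parts, and some of it stands.

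- **Counts by arm are planned, and the named effects enter the modelled total.** This is correct. A reader might infer that the three effects get no comparison by arm at all, and the documents do not support that. What is missing is an event-specific estimate with its uncertainty.
- **Hypothesis 2 is wider than the three effects.** Also correct. It covers overall safety and delirium. Delirium is analysed under Aim 1, and Section 8.a calls an increase in it the main potential risk. Much of Hypothesis 2 therefore has a planned comparison.
- **The plan never says that the observed arm difference will be the effect size.** This stands as a matter of wording. Counts by treatment assignment used to determine power most naturally suggest it, but they would also supply the placebo-arm rate. The instability of the planned size counts against the plan only under the first reading.
- **The 3% versus 2% rates fit poorly.** They come from chronic-insomnia patients, and the package insert itself warns that its rates may not carry over to practice. Daily probing after surgery may well give higher rates. The direction of the difference is then more reliable, as the table shows, but the implied sample size remains unstable.
- **A pilot may treat event-level safety descriptively.** Agreed. A risk difference with an interval is descriptive and asks for no test and no larger sample.

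**Conclusion.** The point holds as a free improvement. The named side effects lack an event-specific effect estimate with an interval, and the one stated use of their counts needs clarifying. If the observed difference were used as the effect size, it would be tied or in the wrong direction in about 54% of trials at the package-insert rates and about 13% at an assumed 20% versus 10%. In the second case the implied n would span about 46 to 1,000 per arm against about 196 needed.

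These figures rest on 40 per arm, two-sided alpha 0.05, 80% power and the rates shown. The 3% versus 2% case is one scenario, for somnolence and fatigue only. Somewhat more than 80 may be randomized, because participants not adherent to the first dose stay in the intent-to-treat set. That would not change the conclusion.

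Two stronger conclusions are not supported. One is that better reporting would let this trial establish no increase in these effects: with half-widths of about 7 to 20 points, the limit is the sample size, and an interval shows that limit without removing it. The other is that phase 3 would be mis-sized as a result: phase 3 is conditional, and nothing in the documents says that it would be sized on these events.

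**What to change.** In Section 7.c, Data Analysis-Specific Aim 2, replace the sentence on specific event types with text to this effect:

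*For fatigue, headache and next-day somnolence, the number and proportion of participants affected at any postoperative assessment will be reported by arm, with the risk difference and its 95% confidence interval (Newcombe). These are estimates; at this sample size they cannot by themselves establish the absence of an increase. Later trials will be powered on the placebo-arm rate, taken with its confidence interval, and on a prespecified smallest difference worth detecting, not on the arm difference observed here.*

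Counting participants rather than events avoids counting the same complaint again at successive assessments. Newcombe's interval suits the very small counts that are possible here. Other specific event types can stay as counts by arm.

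The cost is one sentence's worth of SAP wording and one table, from data already being collected. Sample size, visits and the Aim 1 analyses are unaffected.
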